##### **Secondary Efficacy Analyses**

Supportive analyses will be conducted on the secondary efficacy endpoints described in Section 3.5. Categorical variables will be analyzed using a logistic regression like that described for the primary endpoint. In addition to the point estimate and confidence interval for the difference in proportions for categorical endpoints, odds ratios, corresponding confidence intervals and p-values will be provided. For categorical measures that are recorded over time, separate logistic regression analyses will be conducted at each timepoint.

Continuous secondary efficacy endpoints will be analyzed using a mixed model repeated measures MMRM analysis. The MMRM will include factors for treatment, baseline age group, gender, and scheduled timepoint as well as a random effect for patient. Model based means for each treatment group, model based differences between treatment groups will be provided over time as well as their corresponding confidence intervals and relevant p-values.

For time-to-event data, a two-sided stratified log-rank test will be applied. The stratification factor will be baseline age group (<60 versus  $\geq 60$ ). Estimates of the 25th, 75th percentile and the median (50th percentile) will be provided for each treatment group. Kaplan-Meier Curves and corresponding 95% confidence intervals will be provided as well as p-values based on the stratified log-rank test.

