The primary objective is to assess the efficacy of ATI-450 on hypoxic respiratory failure-free survival in patients with moderate-severe COVID-19 pneumonia at day 14.

Secondary Objectives:

- To assess the clinical efficacy of ATI-450 on respiratory function and survival in patients with moderate-severe COVID-19 pneumonia.
- To assess the safety of ATI-450 in patients with moderate-severe COVID-19 pneumonia.

Exploratory Objectives:

- To Assess the pharmacodynamics of ATI-450 in patients with moderate-severe COVID-19 pneumonia.

Outcome Measures

Primary Efficacy Measure

- Primary treatment responder: defined as any patient who is alive, free of respiratory failure (does not require supplemental oxygen (greater than pre-existing use)) and does not experience a negative intercurrent event on Day 14 of the trial.

An intercurrent event is one that occurs after the first dose of study medication and either precludes the observation of the primary variable/endpoint or affects its interpretation. The following is a list of negative intercurrent events that could occur during this study:

- Death
- Withdrawal from study
- Intubation and ventilation
- Rescue with a non-protocol specified treatment for cytokine release syndrome

The following is a list of positive intercurrent events that could occur during this study:

- Early hospital discharge due to recovery

A patient will be considered a treatment responder if the primary endpoint is missing following a positive intercurrent event. A patient will be considered a treatment non-responder for all observations (missing or not missing) following a negative intercurrent event.

Secondary Efficacy Measures

- Change from baseline in the WHO COVID-19 7-point ordinal scale over time (**BASELINE, DAY 7, DAY 14, DAY 28**).
- All-cause mortality through Day 60 (**DAY 7, DAY 14, DAY 28 AND FOLLOW-UP**.).
- Responder based on 7-point ordinal scale: Greater than 2-point improvement from baseline on the 7-point ordinal scale. (**BASELINE, DAY 7, DAY 14, DAY 28 AND FOLLOW-UP**.).
- Time to discharge from the hospital.

Safety assessments include:

- Adverse events

Exploratory measures include:

- Change in serum cytokine Interleukin (IL)-6 over time (baseline, d7, EOT, d28).
- Change in serum cytokine IL-8 over time (baseline, d7, EOT, d28).
- Change in serum cytokines IL-1 β over time (baseline, d7, EOT, d28).
- Change in serum cytokine Tumor Necrosis Factor (TNF- α) over time.

*EOT: end of treatment

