Sample Size Justification

Data from 20 patients (10 randomized to ATI-450 and 10 to Placebo) provide some preliminary information about the efficacy and safety of ATI-450. No hypothesis will be formally tested. The mean and exact 90% confidence intervals for within-group event rates will be estimated and no between group difference will be estimated.

Randomization and Blinding

Prior to the start of the study, the University of Kansas Medical Center will generate a list of randomization numbers that shall be transmitted to the assigned clinical packaging organization for study medication labeling. The randomization list will be stored with access limited to designated personnel for study medication labeling. The randomization list will be made available, as appropriate, to unblind the database.

In the treatment period, subjects will be assigned to 1 of the 2 treatment groups in a random manner and at a 1:1 ratio stratified by baseline age group (<60 versus \geq 60). At the Day 1 visit an investigational center staff member will assign study medication to eligible subjects by selecting an appropriate Subject Kit. The staff member must select Subject Kits in chronological sequence and in an ascending numerical order starting with the lowest available Subject Kit number. No Subject Kit number may be omitted or reused. The Subject Kit number is the randomization number.

This study uses a double-blind design. The study medications are indistinguishable in appearance, as packaged and labeled.

Analysis populations

- The Full Analysis Set (FAS) will include all patients who have been administered at least one dose of study medication. The FAS will be population used in the primary efficacy analysis. The FAS will also be the population used secondary efficacy analyses and summaries as well as the population used in all safety summaries. The FAS will be analyzed/summarized as randomized when applied to efficacy endpoints. The FAS will be analyzed/summarized as treated when applied to safety endpoints.
- The Per-Protocol population will include all FAS patients who have completed their Day 14 visit and have continued study drug administration through Day 14 or were successfully discharged prior to Day 14. The Per-protocol population will be used for the primary efficacy analysis. Summaries and analyses using the per-protocol population will be done as treated.

Statistical Analysis Methods

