Descriptive statistics (number of observations, mean (standard deviation) or median (minimum, maximum)) will be provided for continuous variables, and counts and percentages will be presented for categorical variables for each group.

Primary Efficacy Analysis

The study is hypothesis generating. The primary assessment of efficacy for this study will be the point estimate and corresponding exact 90% confidence interval for the proportions of responders for the ATI-450 and Placebo groups. All subjects who are alive, free of respiratory failure (do not require supplemental oxygen) by Day 14 of the trial will be considered responders. The point estimate and corresponding 90% confidence interval will be derived based on sample proportions and the Copper-Pearson CIs for proportions for the two groups (categorical data analysis by Alan Agresti, 3rd edition).

Secondary Efficacy Analyses

Binary variables will be analyzed using the method like that described for the primary endpoint. In addition to the point estimate and confidence interval for the difference in proportions for binary endpoints, odds ratios, corresponding confidence intervals will be provided. For binary measures that are recorded over time, separate analyses will be conducted at each timepoint.

Continuous secondary efficacy endpoints will be analyzed by estimating group means and mean difference and 95% CIs at each time point. Missing data will be imputed with the single imputation methods described above (LOCF or WOCF).

For time to discharge from hospital, estimates of the median (50th percentile) will be provided for each treatment group and Kaplan-Meier Curves will be provided. A two-sided stratified log-rank test will be applied. The stratification factor will be baseline age group (<60 versus ≥ 60).

Exploratory Outcomes Analyses

For all the Cytokines, changes over time (baseline, d7, EOT, d28) will be summarized by descriptive statistics and trajectory plots. Any time point after the end of treatment (EOT) will not be measured.

Safety Summaries

AEs will be summarized using table format based on DSMB requirements (attached).

Missing Data Imputation

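### The mean difference in ordinal-scale change ignores the age stratum and the baseline score, so its 95% interval may be wider than it need be

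*SAP*

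**What the plan says.** The SAP, under Secondary Efficacy Analyses, states: "Continuous secondary efficacy endpoints will be analyzed by estimating group means and mean difference and 95% CIs at each time point". It names no covariate. Among the secondary measures listed in the SAP, only "Change from baseline in the WHO COVID-19 7-point ordinal scale over time" is neither binary nor time-to-event, so the sentence must apply to it, although the SAP does not say so outright. Scores are analysed at Days 7, 14 and 28 against baseline.

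Four other places bear on the point:

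- SAP, Randomization and Blinding: subjects are allocated "at a 1:1 ratio stratified by baseline age group" (under 60 versus 60 and over).
- SAP, Secondary Efficacy Analyses, on the log-rank test for time to discharge: "The stratification factor will be baseline age group". The stratum is therefore used for one secondary endpoint and not for the other.
- Protocol section 15.3: "The MMRM will include factors for treatment, baseline age group, gender, and scheduled timepoint as well as a random effect for patient". The protocol adjusted for age group and gender, but not for the baseline value of the outcome.
- Protocol section 10.1.1 and the schedule of events: the ordinal scale is scored on Hospital Day 1, the baseline.

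The SAP's Sample Size Justification says that between-group differences will not be estimated. That sits awkwardly with the mean difference planned here.

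**The concern.** Stratified randomisation removes most of the stratum's contribution from the treatment difference. If the analysis then leaves the stratum out, that variation stays in the residual and the standard error is too large for the design. A nominal 95% interval will then cover more than 95% of the time if age predicts the outcome. The SAP gives no reason for dropping a term that the protocol had.

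The baseline score is a separate matter. A change score subtracts baseline with its slope fixed at 1. If the true slope is different, some chance baseline imbalance stays in the estimate, and a fitted slope would remove it. With 10 per arm the baseline difference has a standard error of sqrt(2/10) = 0.45 baseline SD, so imbalances are not rare.

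What is at stake is precision. In a 20-patient study that reports estimates and not formal tests, the interval is the result.

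**Working it through.** Neither document states an SD, width or power for this mean difference, so there is no planned figure to reproduce.

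**Inputs from the documents.** The sample size is "Data from 20 patients (10 randomized to ATI-450 and 10 to Placebo" in the SAP. Age group is the stratum. Patients must be hospitalised (protocol 5.1.4) and not intubated (5.2.10), so on the Appendix B scale baseline scores lie at about 3 to 5, while follow-up scores can range from recovery to death (8).

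**Inputs assumed.** These are k = baseline SD / follow-up SD, r = baseline to follow-up correlation, and the age effect in follow-up SDs. Age strata are taken as equal in size and balanced 5/5 by arm; no block size is stated. Scores are treated as normal, with no imputation.

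**1. Raw interval.** Half-width = t(0.975, 18) × SD × sqrt(2/10) = 2.101 × 0.447 × SD = 0.94 SD of the change score.

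**2. Baseline score alone.** Width ratio, adjusted to raw = sqrt[(1 − r²)/(1 + k² − 2rk)] × t(17)/t(18) × sqrt(1 + 1/16). The last two factors are 1.004 and 1.031.

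- k = 1, r = 0.5: sqrt(0.75/1.00) = 0.866, giving 0.90.
- k = 1, r = 0.7: 0.922, giving 0.95.
- k = 0.75, r = 0.5: sqrt(0.75/0.8125) = 0.961, giving 0.995.
- k = 0.5, r = 0.5: sqrt(0.75/0.75) = 1, giving 1.035, which is wider.

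The true slope is r/k. In the last case it is 1, so the change score already makes the best linear correction and fitting the slope only costs.

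**3. Age group alone, balanced.** Width ratio = sqrt(1 − R²) × 1.004, where R² is the share of the variance of change explained by age group. It is 1.004 at R² = 0, 0.98 at 5%, 0.95 at 10% and 0.90 at 20%. Break-even is R² = 1 − 1/1.0042² = 0.8%.

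**4. Both covariates.** Simulated width ratios, 8,000 trials per setting, 10 per arm:

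| k | r | No age effect | 0.5 SD | 1 SD |
|---|---|---|---|---|
| 0.5 | 0.2 | 0.99 | 0.96 | 0.88 |
| 0.5 | 0.5 | 1.04 | 0.99 | 0.89 |
| 0.5 | 0.7 | 1.00 | 0.94 | 0.81 |
| 1.0 | 0.2 | 0.80 | 0.79 | 0.74 |
| 1.0 | 0.5 | 0.90 | 0.87 | 0.80 |
| 1.0 | 0.7 | 0.96 | 0.91 | 0.79 |

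**5. Coverage of the raw 95% interval.** In the same simulations it was 95.0 to 95.9% at a 0.5 SD age effect and 96.4 to 98.1% at 1 SD. The adjusted interval covered 94.4 to 95.5% throughout. Monte Carlo error is about sqrt(0.95 × 0.05/8000) = 0.24 percentage points.

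**The case against.** An unadjusted difference from a randomised comparison is valid. This one is a secondary endpoint in a hypothesis-generating study with no formal test and no decision rule attached to the interval. Even a 13% reduction takes the half-width only from 0.94 to about 0.82 SD, which is still imprecise. All of that stands, and it keeps the point minor.

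Three stronger readings are tempting, and the documents do not support them.

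- **That adjustment would certainly narrow the interval.** A reader might use sqrt((1 + r)/2), which gives 0.81, 0.87 and 0.92 for r = 0.3, 0.5 and 0.7. That formula needs equal baseline and follow-up SDs (k = 1). The entry criteria narrow the baseline range, which points to k below 1, where the gain from baseline can vanish or reverse.
- **That a change score over-corrects for baseline.** This is true only when r/k is below 1. At k = 0.5, r = 0.7 the slope is 1.4 and the change score under-corrects.
- **That the raw difference is biased by chance imbalance.** Over repeated randomisation it is unbiased, and its interval already allows for such imbalance. What remains is a conditional argument. With a slope of 0.5, an observed imbalance of 0.45 baseline SD shifts the difference by about 0.22 SD; with a slope of 1, the shift is nil.

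It can also be said that the SAP disclaims between-group estimation altogether. That sentence is attached to event rates, and the later section expressly plans a mean difference. The two statements need reconciling; they do not remove the point.

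**Conclusion.** The concern holds as a question of precision. The planned mean difference leaves out the randomisation stratum and the baseline score, both of which are available. Over the assumed range (k 0.5 to 1, r 0.2 to 0.5, age effect 0 to 1 SD), adjusting for both changes the interval width by about −26% to +4%; the settings at r = 0.7 fall inside those limits. The balance favours adjustment, since the possible loss is small.

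The age term is the stronger half. It is part of the design, the protocol had it, it pays for itself at about 1% of variance explained, and leaving it out makes the nominal 95% interval conservative if age is prognostic. The case for the baseline score is weaker and depends on the SD ratio. The size of either effect rests on quantities that the documents do not give, so only the possibility of wider intervals can be asserted. No bias is shown.

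**What to change.** In the SAP's Secondary Efficacy Analyses, specify for each visit a linear model of the ordinal score on treatment, baseline score and age group (<60, ≥60). Report the adjusted mean difference with its 95% interval beside the raw group means. With baseline in the model, the treatment estimate is the same whether the score or its change is the outcome. If only one covariate is acceptable, keep age group.

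Add a sentence explaining the departure from the protocol's MMRM, since this model omits gender and the repeated-measures structure. Reconcile the Sample Size Justification's statement that no between-group difference will be estimated with the mean difference planned here.

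The cost is one model statement, two degrees of freedom, and an interval up to about 4% wider if age has little effect and the baseline slope is near 1. No new data are needed.

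### The SAP does not say how in-hospital death enters the time-to-discharge analysis; if deaths are censored, the Kaplan-Meier curve overstates discharge and excess deaths are understated or hidden

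*SAP*

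**What the plan says.** Under Secondary Efficacy Measures the SAP lists "Time to discharge from the hospital" and does not say whether the event is discharge alive. Under Secondary Efficacy Analyses, "estimates of the median (50th percentile) will be provided for each treatment group and Kaplan-Meier Curves will be provided". The comparison follows: "A two-sided stratified log-rank test will be applied", and "The stratification factor will be baseline age group" (under 60 against 60 and over). No censoring rule and no rule for death is given. Protocol Section 15.3 names the same tools for time-to-event data and is equally silent.

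Both documents list death first among the negative intercurrent events (SAP, Primary Efficacy Measure; protocol Section 15.5). The consequence is spelled out for two kinds of endpoint:

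- Primary and binary or categorical endpoints: the patient is a non-responder.
- Continuous endpoints: the worst earlier value is carried forward.

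Neither document extends the rule to time-to-event endpoints. Mortality is a separate secondary measure: "All-cause mortality through Day 60". On size and intent: "Data from 20 patients (10 randomized to ATI-450 and 10 to Placebo) provide some preliminary information", and "No hypothesis will be formally tested".

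**The concern.** Discharge is a favourable event and death makes it impossible. Kaplan-Meier censoring assumes that a censored patient would have gone on to have the event at the same rate as those still at risk. Applied to a death, it assumes that the patient would eventually have gone home. The curve then describes discharge in a population where nobody dies, not the share of randomised patients who left hospital alive.

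Deaths are foreseeable in patients enrolled with hypoxic respiratory failure, and with 10 patients per arm each death is 10 percentage points. Time to discharge is the only time-to-event analysis in the SAP and the only one with a named significance test. If the death rule is left open, it may be chosen after the data are seen, and the choice can change the direction of the result.

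**Working it through.** The documents give no death rate, event count or hazard ratio for this endpoint, so there is no plan figure to reproduce. From the SAP come 10 patients per arm, 1:1 allocation and follow-up to Day 60. All event times and death rates below are assumptions. The log-rank figures are unstratified.

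**1. One arm of 10.** Discharges on Days 3, 4, 6, 7, 9, 10, 12, 14; deaths on Days 5 and 8. Kaplan-Meier: S(t) = product of (1 − d/n) over discharge days, with proportion discharged = 1 − S.

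- Deaths censored: (9/10)(8/9) = 0.800 by Day 4. The Day 5 death leaves 7 at risk, and (6/7)(5/6) brings S to 0.571 by Day 7. The Day 8 death leaves 4 at risk, and (3/4)(2/3)(1/2)(0/1) brings S to 0 at Day 14. Estimated discharged: 100%.
- Deaths kept at risk as undischarged: S falls by 0.1 at each discharge, to 0.2 at Day 14. Estimated discharged: 80%, which is the true 8 of 10.
- Median (first day with S ≤ 0.5): Day 9 both ways (S = 0.429 and 0.500). Software that averages when S equals exactly 0.5 gives (9 + 10)/2 = 9.5 for the second.

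**2. Size by mortality.** Simulated arms of 10; discharge times gamma with mean 10 days; a set share of patients die, at times uniform over Days 3 to 20; deaths censored.

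| Mortality | Kaplan-Meier discharged by Day 28 | Actually discharged | Excess (points) |
|---|---|---|---|
| 10% | 97% | 90% | 7 |
| 20% | 94% | 80% | 14 |
| 40% | 84% | 60% | 24 |

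A re-run with gamma shapes 2 to 4 gave 96–98% against 88–89%, 93–95% against 78–80%, and 83–85% against 59–60%.

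**3. Direction between arms, same set-up.** For 40% against 10% mortality, the true gap in discharge is 90 − 60 = 30 points and the censored curves show 97 − 84 = 13. Across those shapes the mean log-rank Z for the high-death arm was about −0.85 with deaths censored and about −1.45 with deaths kept at risk. The harm is attenuated, not reversed.

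**4. What a reversal needs.** Both arms have the same discharge hazards: 40% of patients slow (mean 25 days) and 60% fast (mean 8 days). Arm A has more deaths.

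- *Deaths only among slow patients.* Daily death hazard 0.08 in A and 0.02 in B, so 0.4 × 0.08/(0.08 + 0.04) = 27% against 0.4 × 0.02/(0.02 + 0.04) = 13% die before discharge. With deaths censored, mean Z favours A: +0.22 at 10 per arm and +2.84 at 1,000 per arm. At 1,000 per arm, the Day 28 curves read 0.92 (A) against 0.87 (B), while 0.71 against 0.80 were actually discharged.
- *Deaths independent of recovery.* Hazards 0.03 and 0.0075, so about 29% against 10% die. Mean Z is 0.01. At 1,000 per arm, the curves read 0.85 in both arms, while 0.67 against 0.80 were actually discharged. The excess deaths are hidden and A gains no advantage.
- *Deaths kept at risk to Day 60.* Mean Z at 10 per arm turns against A in both settings: −0.45 and −0.65.

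**5. Why the rule must be written down.** Arm A: discharges on Days 5, 6, 7, 8, 9, 10, 12 and deaths on Days 4, 6, 8. Arm B: the same seven discharges, then Days 20, 24, 28. With O − E = sum of (observed − expected discharges in A) and Z = (O − E)/√V:

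| Rule for death | Discharged by Day 14, A / B | Median, A / B | O − E for A | Z | p |
|---|---|---|---|---|---|
| Censored | 100% / 70% | 9 / 9 | 1.78 | 1.78/√2.80 = 1.07 | 0.29 |
| Undischarged to Day 60 | 70% / 70% | 9 / 9 | −1.85 | −1.85/√3.88 = −0.94 | 0.35 |
| Counted as leaving hospital | 100% / 70% | 7 / 9 | 3.40 | 3.40/√3.39 = 1.84 | 0.065 |

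The same data point in different directions under different rules, and the SAP permits all three.

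**The case against.** The strongest reply is that the SAP is silent, not wrong. Keeping deaths undischarged to Day 60 is itself a Kaplan-Meier and log-rank analysis and fits the text as written. That stands: a reader might infer that the SAP treats dead patients as still dischargeable, but it does not say so. Censoring at death is only the usual default.

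A reader might also infer that the arm with more deaths will look better. Neither the documents nor the checks support that as a general claim. In steps 2 and 3 the censored curve falls as mortality rises, and the comparison still runs against the high-death arm. A reversal needs deaths concentrated in patients who would have gone home late. That is plausible in this disease, but nothing in the documents establishes it, and at 10 per arm the simulated tilt was small.

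The SAP reports the median and the curve, not a Day 28 proportion, and the median barely moved in the worked examples when deaths were censored instead of kept undischarged. That stands for the median, but the overstatement shows directly on the published curve.

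Finally, the trial is hypothesis-generating, no alpha is attached to the test, and mortality is reported separately, so excess deaths would be visible elsewhere. This lowers the stakes. It does not supply the missing rule.

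**Conclusion.** The point holds as a gap in specification with a conditional bias. No section of either document says how in-hospital death enters time to discharge. If deaths are censored, the curve overstates discharge in any arm with deaths, by roughly 7, 14 and 24 percentage points by Day 28 at 10%, 20% and 40% mortality under the assumed event times. The log-rank comparison then understates or hides harm from excess deaths, and favours the arm with more deaths only when those deaths fall in patients with late expected discharge. The in-hospital death rate and the link between death and recovery time are assumptions throughout. The matter is worth correcting because the remedy is cheap and the choice of rule can change the sign of the comparison, but it bears on one secondary endpoint only.

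**What to change.** Add to Secondary Efficacy Analyses that the event is discharge alive, and choose one of two rules before unblinding:

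- keep patients who die in hospital in the risk set as undischarged to Day 60, for the curve, the median and the stratified log-rank test; or
- report the cumulative incidence of discharge with death as a competing event, compared by a stratified Gray test.

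In either case, show deaths beside the discharge curve, by arm. The first option keeps every tool that the SAP already names. The cost is about one SAP sentence, and both options are available in standard SAS procedures. The downside is that the discharge figures will look somewhat less favourable than under censoring.

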##### 3.1.2 Secondary Objectives

To assess the clinical efficacy of ATI-450 on respiratory function and survival in patients with moderate-severe COVID-19

To assess the safety of ATI-450 in patients with moderate-severe COVID-19.

To assess the anti-inflammatory and immune effect of ATI-450

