#### 3.2 ENDPOINTS

To assess the pharmacodynamics of ATI-450 in patients with moderate-severe COVID-19 (based on changes in cytokine and biomarkers)

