##### 3.2.2 Secondary Endpoints

What is being measured	Measurement time frame	Measurement Tool
Change in 7 point-ordinal scale	Baseline, Day 3, Day 7, Day 14, Day 28 and follow-up.	Using WHO COVID-19 Ordinal scale measuring: Proportion and time to patients with greater than 2 point improvement on the 7 point categorical scale

Change in oxygen saturation-normalization	Baseline and continuous throughout hospitalization	Peripheral capillary pulse oximeter to measure: SpO 2 /FiO 2 ratio over time, sustainment of normalization in 24 hours, and relative shifts in SpO 2 /FiO 2 categories (<235, between 235 and 315, greater than 315) over time
Need for advanced respiratory care	Baseline and continuous throughout hospitalization	Derived from medical record: time of intubation in the ICU, duration of ICU care in days, duration of overall hospitalization in days
All-cause mortality	Baseline and through d60	Noted in patient medical record
Number and percent of adverse events (AEs) and serious adverse events (SAEs); mean change from baseline lab values, vital signs, and ECG	Baseline through day 14 or at discharge <d14, at d28 ±3, d45 ±3 and d60 ±3 (lab values will be examined up to d45) 	CTCAE v5.0; changes in CBC, CMP, Mg, PT/INR, PTT, GGT, hsCRP, D-dimer, LDH, ferritin, creatine kinase, troponin-i, procalcitonin; standard vital signs measurement with pulse ox; ECG
Proportion of participants with normalization of fever for 24h	Baseline through day 14 or at discharge <d14	Standard daily vital measurement and obtained from patient medical record
Development of new bacterial or fungal infection (AE of Special Interest)	Continuous throughout hospitalization	Noted in patient medical record
Incidence of ARDS  through day 14 or at discharge <d14	From day 1 though day 14 or at discharge <d14	Noted in patient medical record
Change in plasma cytokines IL-1β, IL-6, IL-8 and TNF-α	Baseline, day 3, day 7 (or discharge <d7), day 14 (or discharge >d7 and <d14)	Plasma collected from blood and assayed on Luminex panel performed by KUMC BBV Core

 For clarification, lab values will be collected at baseline, day 3, day 7 (or discharge <d7), day 14 (or discharge >d7 and <d14), at day 28 ±3, day 45 ±3. Vital signs, pulse ox will be collected baseline through day 14 or at discharge <d14, at d28 ±3, d45 ±3 and d60 ±3 (lab values will be examined up to d45)

 ARDS Criteria:

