#### 14.1.2 CYTOKINE SECONDARY ENDPOINT

At baseline (d1), d3, d7 , d14 or discharge if <d14 and d28, we will collect 1 tube of blood to isolate serum. Blood will be collected on the floors, sent to the clinical lab and transported to the KUMC Biospecimen and Biomarker Validation (BBV) Core in the Biospecimen Repository Core Facility (BRCF) within 2 hour of being drawn (within 4 hours from outside hospital). All work described is approved by the University of Kansas IBC.

Samples will be batch assayed in order to minimize variations between patients sampled on different days. Cytokines to be assayed will include: IL-1 $\beta$ , IL-6, IL-8, TNF $\alpha$ .

**Luminex or MSD Assays** - Circulating levels of cytokines of interest in serum or plasma will be quantified using multiplexed fluorescent magnetic bead-based immunoassays (Millipore-Sigma) following manufacturer's protocols. Briefly, an overnight bead capture will be performed at 4 °C in black-walled 96-well plates on a plate shaker at the specified dilution of the serum/plasma. Detection and reporter antibodies (streptavidin-conjugated phycoerythrin) will be added on day 2 and incubated at room temperature with shaking. A Bioplex 200 instrument (BioRad) will be used to measure the mean fluorescent intensity (MFI) values for each marker for each test sample and known standards. Standard curves generated using MFI versus concentration data will be used to calculate the cytokine levels in each sample.

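### IL-1β, IL-6, IL-8 and TNF-α are a secondary endpoint in the protocol but exploratory and descriptive-only in the SAP, so no arm difference or interval is planned for them

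*SAP*

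**What the plan says.** **Protocol.** Section 3.1.2, like the Protocol Summary, has the secondary objective "To assess the anti-inflammatory and immune effect of ATI-450". The Section 3.2.2 table of secondary endpoints contains "Change in plasma cytokines IL-1β, IL-6, IL-8 and TNF-α", at baseline and days 3, 7 and 14 (or discharge). Section 14.1.2 is headed "CYTOKINE SECONDARY ENDPOINT" and names the same four. The opening of Section 15 says that objectives will generally be assessed by point estimates with confidence intervals. Section 15.3 adds: "Continuous secondary efficacy endpoints will be analyzed using a mixed model repeated measures MMRM analysis", and "model based differences between treatment groups will be provided over time as well as their corresponding confidence intervals".

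**SAP.** The secondary objectives cover clinical efficacy and safety only. A pharmacodynamic objective remains as exploratory, and the four cytokines are listed as exploratory measures. For these, "changes over time (baseline, d7, EOT, d28) will be summarized by descriptive statistics and trajectory plots". The SAP's descriptive statistics for a continuous variable are the count with mean (SD) or median (range), by group. For continuous secondary efficacy endpoints, by contrast, it plans group means, the mean difference and 95% CIs at each time point.

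**The concern.** The two documents put the same measurements in different tiers, and the tier decides the analysis. In the SAP a continuous secondary endpoint gets an arm difference with an interval; an exploratory cytokine does not. The SAP does not explain the move.

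Cytokine suppression is the stated rationale for the drug (protocol Section 1.2) and part of the dose justification (Section 4.2). Change within one arm cannot isolate a drug effect here: dexamethasone is allowed (exclusion criterion 5.2.4), and Section 4.4 accepts that evolving standard of care may confound results. The randomised contrast addresses this, and it is what the SAP leaves out.

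The change of tier also has side effects. The SAP's carry-forward rules (LOCF and WOCF) and its assignment to the Full Analysis Set are written for secondary endpoints, so the cytokines have no stated missing-data rule or analysis population.

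**Working it through.** **1. Comparison of the texts**

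| Item | Protocol | SAP |
|---|---|---|
| Anti-inflammatory objective | Secondary (Summary, 3.1.2) | Absent |
| The four cytokines | Secondary (3.2.2, 14.1.2) | Exploratory |
| Other cytokines | Separate exploratory list of 13 (3.2.3, 14.1.3.1) | Not listed |
| Planned output | Estimates and intervals (15); by natural reading, MMRM arm differences (15.3) | Per-arm summaries and plots |
| Sampling times | Baseline, days 3, 7, 14 (3.2.2); day 28 as well in 14.1.2 | Baseline, day 7, EOT, day 28; day 3 dropped |

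The protocol's exploratory cytokines are a different set, so placing these four in the secondary table looks deliberate. The MMRM link is an inference: Section 15.3 refers to "secondary efficacy endpoints described in Section 3.5", and there is no Section 3.5. It is the natural reading, because the cytokines stand in the only table of secondary endpoints. The general statement at the start of Section 15 does not depend on it.

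Cytokines with a planned arm difference or interval under the SAP: 0 of 4.

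**2. Precision if an arm difference is added**

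Neither document gives an SD, effect size or precision target for the cytokines, so there is no planned figure to reproduce.

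*Unadjusted, by the SAP's own method for continuous secondary endpoints.* The 95% half-width in SD units is t(0.975, 2n−2) × √(2/n).
- n = 10 per arm (SAP): 0.94 SD.
- n = 18 per arm (protocol Section 15.1): 0.68 SD.

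*Log scale, adjusted for log baseline and age stratum.* SE = SD × √(2(1−ρ²)/10). Four parameters leave 20 − 4 = 16 degrees of freedom, and t(0.975, 16) = 2.120. The interval for the ratio is ×/÷F, with F = exp(2.120 × SE). SD and ρ are assumed, and every patient is assumed to have samples.

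- Best case (SD 0.8, ρ 0.6): SE = 0.8 × √0.128 = 0.286; F = exp(0.607) = 1.83.
- Middle (SD 1.15, ρ 0.45): SE = 1.15 × √0.1595 = 0.459; F = exp(0.974) = 2.65.
- Worst case (SD 1.5, ρ 0.3): SE = 1.5 × √0.182 = 0.640; F = exp(1.357) = 3.88.

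An observed ratio r excludes 1 only if r × F < 1, that is r < 1/F: 0.55, 0.38 and 0.26 respectively. An observed ratio of 0.6 does not exclude 1 even in the best case (0.6 × 1.83 = 1.10).

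**The case against.** **The protocol is mixed on cytokines.** Section 3.2 ties pharmacodynamics to cytokine and biomarker changes, and the Summary calls the pharmacodynamic objective exploratory. This stands in part. But the Summary lists that objective in addition to the secondary anti-inflammatory one, and Sections 3.2.2 and 14.1.2 place these four explicitly.

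**The SAP avoids between-arm estimates.** Its sample-size section says that no group difference will be estimated. In context that sentence concerns event rates. The SAP still plans mean differences, odds ratios and a stratified log-rank test for secondary endpoints.

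**Ten per arm is too few, and the study is hypothesis generating.** This limits what can be concluded and argues against a p-value. It does not argue against showing the uncertainty: the SAP gives an interval for ordinal-scale change in the same 20 patients.

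**Selective demotion.** A reader might infer that the cytokines were singled out. The documents do not support this. The SAP cut back broadly: the sample size is 20 against 36 in protocol Section 15.1, the MMRM is gone for every continuous endpoint, and the oxygenation, ICU, fever, ARDS and infection endpoints are missing from its efficacy measures. Nothing shows that the change was made with knowledge of results.

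**The objective cannot be answered.** A reader might infer this too, but it is too strong. Both randomised arms are displayed. If n, mean and SD are reported, an unadjusted difference and interval can be recovered; if median and range are reported, they cannot.

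**Conclusion.** The mismatch is real and unexplained. A protocol secondary endpoint, tied to a protocol secondary objective, has no planned arm difference or interval in the SAP. What is lost is a pre-specified, preferably baseline-adjusted, estimate with its uncertainty. The primary result is unaffected.

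The gain from adding it is modest. Under the assumptions above, the 95% interval is about ×/÷1.8 to ×/÷3.9, and missing samples would widen it. The thresholds of 0.55 and 0.26 apply to observed ratios; a true ratio at the threshold would give only about even odds of excluding 1. It would therefore be wrong to say that the descriptive plan discards a likely conclusive result.

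A reader might also argue that cytokines fall with recovery in any case. The documents do not say so; Section 1.1.1 only links raised levels to severe or fatal disease. The case rests on concomitant treatment and changing standard of care. The change should be made, but it is not critical to the trial.

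**What to change.** - Restore the anti-inflammatory objective and the secondary tier of the four cytokines in the SAP.
- At each on-treatment visit with samples, report the ATI-450 versus placebo difference with the 95% CI that the SAP already uses for continuous secondary endpoints. A ratio from a model on log concentration, adjusted for log baseline and age stratum, is preferable. Give no p-value, and keep the plots as support. This model is neither the protocol's MMRM nor the SAP's simple mean difference, so it must be written out.
- Name the analysis population (FAS), and say whether LOCF/WOCF values enter the model.
- If the lower tier is intended, record and justify it as a change from protocol Section 3.2.2, and still add the arm difference with its interval.
- Reconcile the sampling times. The SAP's exploratory section lists day 28 but then says that nothing after EOT is measured, and it drops the protocol's day 3 draw. Correct the protocol's reference to Section 3.5.

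Cost: SAP wording and one simple model per cytokine, on samples already planned. The downside is wide intervals.
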